6.2.5 Analysis of the primary efficacy variable

The primary analysis will be based on the time from randomization to the first occurrence of any of the components of the primary efficacy outcome (independently adjudicated), using the ITT analysis set and ITT data scope.

The null hypothesis will be:

$H_{0, PE}: S_R(t) = S_A(t)$ for all time points $t \geq 0$, (i.e., "there is no difference between the rivaroxaban added to ASA group and the ASA alone group regarding the primary efficacy outcome for all time points"),

and the one-sided alternative hypothesis will be:

$H_{1, PE}: S_R(t) > S_A(t)$ for at least one time point $t \geq 0$, and $S_R(t) \geq S_A(t)$ for all time points $t \geq 0$, (i.e., "there is a difference between the two groups in favor of rivaroxaban regarding the primary efficacy outcome for at least one time point"),

where S_R denotes the survival function of the rivaroxaban added to ASA group and S_A denotes the survival function of the ASA alone group.

The rivaroxaban added to ASA group will be compared to the ASA alone group using a log-rank test stratified by type of procedure and clopidogrel use ((i.) surgical vs. (ii.) endovascular with clopidogrel vs. (iii.) endovascular without clopidogrel per IxRS assignment) with treatment as a fixed factor. Superiority of rivaroxaban over placebo will be declared, if the associated one-sided null hypothesis is rejected in favor of rivaroxaban at the 2.5% significance level.

Kaplan-Meier (KM) estimates of cumulative risk and cumulative hazard functions will be provided to evaluate the timing of event occurrence in the different treatment groups and the consistency of the respective treatment effects for all time points.

The following SAS program code will be used for the log-rank test and Kaplan-Meier estimates:

Statistical Analysis Plan

Protocol No.: **BAY 59-7939 / 17454**

Page: 21 of 36

```
PROC LIFETEST DATA = <dataset> ALPHA=0.05 METHOD=KM NELSON;
STRATA stratum / GROUP=trtgrp TEST=(LOGRANK) TREND;
TIME ttevalue * ttecnr(0);
RUN;

/*
where
dataset = name of dataset including all ITT subjects
trtgrp = variable coding randomized treatment group
ttevalue = time to first occurrence of primary efficacy outcome event
ttecnr = censoring index (0 = right-censored, 1 = event)
stratum = variable for stratification factor */
```

The relative risk reduction (RRR) will be estimated using a Cox proportional hazards (Cox PH) model, stratified by type of procedure and use of clopidogrel per IxRS assignment, with treatment as the only covariate. The point estimate and corresponding 95% confidence interval (CI) for the hazard ratio (HR, rivaroxaban added to ASA vs. ASA alone) will be reported. The plausibility of proportional hazards assumption will be assessed by visually comparing the plot of the log of cumulative hazard between treatments and by additionally adding a treatment by logarithm-transformed time interaction into the Cox PH model.

The following SAS program code will be used for the Cox proportional hazards model:

```
PROC PHREG DATA = <dataset>;
MODEL ttevalue * ttecnr(0) = trtgrp / RL TIES=EFRON ALPHA=0.05;
STRATA stratum;
RUN;

/*
where
dataset = name of dataset including all ITT subjects
trtgrp = variable coding randomized treatment group
ttevalue = time to first occurrence of primary efficacy outcome event
ttecnr = censoring index (0 = right-censored, 1 = event)
stratum = variable for stratification factor */
```

Additional procedure options controlling the output may be added to the program codes.

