
Plan for statistical analysis
	
The primary efficacy analyses will be based on the intent-to-treat (ITT) population using adjudicated results. The rivaroxaban plus study ASA group will be compared to the placebo plus study ASA group using a stratified log rank test. Kaplan-Meier curves for the cumulative incidence risk and cumulative incidence functions will be provided to evaluate the timing of event occurrence. Relative risk reduction will be estimated with the stratified Cox proportional hazards model.
 
Secondary efficacy outcomes will be analyzed using similar methods as for the primary efficacy analysis. Testing will be performed in an hierarchical order.
 
The analysis of the primary safety outcome will be similar to those described for the primary efficacy outcome.
 
There will be one formal interim analysis to assess efficacy and allow for stoppage if overwhelming superiority is detected (<math>p < 0.001</math>), which will occur when approximately 67% of the planned primary efficacy outcomes have accrued.

 Text modified with Protocol Amendment 4 (change no. 8) and Protocol Amendment 5 (see change no 2).

Anticipated total study duration and study duration per patient	Total study duration: ~42 months
	Enrollment period: ~18 months
	Treatment duration for last patient randomized: ~24 months
	Mean treatment duration per patient: ~30 months
	Maximum treatment duration per patient: ~42 months
	The study will be event-driven and these timelines may vary depending on the enrollment rate and event rate in the study.

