4.5.3 Censoring rules for time-to-event variables

All efforts will be made to collect complete data for all subjects randomized in this study including visits by telephone contact.

Censoring rules for analyses according to the ITT principle

The censoring rule for time to first event analyses depends on the type of endpoint, thereby distinguishing between clinical events endpoints (primary efficacy composite and component, secondary efficacy and bleeding events) and CV-death / all-cause mortality.

Statistical Analysis Plan

Protocol No.: **BAY 59-7939 / 17454**

Page: 12 of 36

	Primary efficacy composite and components other than CV-death	All-cause mortality, CV-death
If the subject was randomized but has no post-randomization clinical event ascertainment date the subject will be censored :	At the randomization date + 1 day	Earlier of last contact alive date or ECOD If no last contact alive date, use the randomization date +1 day
Else, if the subject has withdrawn from the study but objected to further data collection the subject will be censored :	At the earlier date of the last clinical event ascertainment date (LCEAD), date of objection to further data collection or ECOD	Earlier of last contact alive date from public sources or ECOD If no last contact alive date from public sources, use the earlier date objection to further data collection or ECOD
Otherwise, the subject will be censored :	At the earlier date of last clinical event ascertainment date, date when patient died or ECOD	At the earlier date of last contact alive date or ECOD

Censoring rules for analyses according to the on-treatment principle

For on-treatment analyses (primary analysis for time to bleeding events, sensitivity analysis for primary efficacy endpoint and all secondary efficacy endpoints), patient with at least one dose of study medication and without documentation of an event within the on-treatment data scope will be censored similarly to the ITT data scope except that the date of last dose of study treatment + 2 days will be used as the cap for the time scope instead of ECOD.

Censoring rules for analyses according to the overall study duration principle

Above censoring rules for ITT data scope apply except that the date of last clinical event ascertainment or last contact alive will be used as the cap for the time scope instead of ECOD.

See [Appendix A](#) for additional details.

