4.6 Determination of sample size

The study is event-driven and it is estimated that approximately 6,500 patients (3,250 per treatment group) need to be randomized in order to have 1,015 patients experiencing a confirmed primary efficacy outcome event. This number of events will allow the demonstration of superiority of rivaroxaban compared to placebo with regard to the primary outcome with a power of 90% and a one-sided level of significance $\alpha=0.025$ under the following assumptions:

- The effect size (Hazard Ratio (HR)) for rivaroxaban plus ASA vs. ASA alone is $HR=0.80$.
- The annualized event rate in the control arm is approximately 7.5% per year.
- The rate of patients with permanent discontinuation of study drug (rivaroxaban plus ASA switching to ASA alone or an equally effective treatment regimen) is approximately 5.5% 1st year, 8% 2nd year, 12% 3rd year (4% 1st half year + 8% 2nd half year), and 8% every half year afterwards.

Statistical Analysis Plan

Protocol No.: **BAY 59-7939 / 17454**

Page: 13 of 36

- The rate of patients lost to follow-up or with non-CV death is approximately 1.5% per year.
- The duration of the enrollment period is 18 months (approximately 15% 1st 6 months, 30% 2nd 6 months, 55% 3rd 6 months) and 2 years of follow-up from last patient-randomized until the ECOD.

The number of patients enrolled may be adjusted and the study duration may be adapted based on a blinded review of the observed overall event rate of confirmed primary efficacy outcomes during the study.

Sample size estimation was based on PASS 11 ([Hintze 2011](#)).

5. Analysis Sets

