6.2.6 Analysis of secondary efficacy variables

If the primary efficacy outcome is statistically significant, the secondary efficacy outcomes will be tested in a sequential manner according to the order as listed in Section 6.2.2 with one-sided alpha of 0.025. If an individual test during any step is not statistically significant, further treatment comparison may continue (i.e., reporting of p-values) but significance will not be claimed. This hierarchical testing procedure will control the global Type 1 error level.

Statistical Analysis Plan

Protocol No.: **BAY 59-7939 / 17454**

Page: 22 of 36

The analysis of the secondary variables will be based on the ITT analysis set and ITT data scope, including events as adjudicated by the ICAC or reported by investigators if not being adjudicated.

The statistical hypotheses for the secondary efficacy outcomes are defined similarly as for the primary efficacy outcome. The analysis methods will be similar to those described for the primary efficacy outcome.

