6.6 Benefit/Risk Assessment

The benefit-risk analyses are structured to allow an integrated evaluation of the key benefits and risks in the study. They are complementary to the efficacy and safety analyses described previously in this document and not intended for hypothesis testing. These analyses will be performed in patient populations with the same follow up. Details of these analyses will be described in a separate document (supplemental statistical analysis plan for benefit-risk).

The benefit-risk evaluation will be based on the comparison of the time-to-first-event rates (rivaroxaban added to ASA vs. ASA alone), for events intended to be prevented (benefits) and events that may be caused (risks). Individual outcome measures balanced and weighed by clinical significance and severity will be compared to evaluate the trade-off between prevention of thrombotic vascular events versus harm (i.e. bleeding). These outcome measures include the individual components of the primary efficacy outcome, risk measurements include the hemorrhagic events of the efficacy endpoint and bleedings according to TIMI classification. To have a comprehensive benefit-risk evaluation, several quantification methods will be used.

Results of the above analysis do not preclude additional benefit/risk assessment in other endpoints. The overall benefit-risk profile of the study drug will be interpreted in consideration of the totality of the data.

7. Document history and changes in the planned statistical analysis

Version	Date	Action
Draft SAP submitted to FDA	12 June 2015	
Version 1.0	7 April 2016	Updates based on protocol amendment #4 and FDA feedback on planned sensitivity analyses to assess the impact of missing data
Version 2.0	14 May 2018	
• Order of secondary efficacy endpoints were changed according to Global Integrated Clinical Study Protocol version 3.0• Efficacy cut-off date and censoring rules for efficacy endpoints were modified in

Statistical Analysis Plan

Version	Date	Action

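### The SAP labels Kaplan-Meier estimates as cumulative risk while censoring at death, which overstates absolute risk for endpoints that do not contain all-cause death

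*SAP*

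**What the plan says.** SAP 6.2.5 plans, for the primary composite: "Kaplan-Meier (KM) estimates of cumulative risk and cumulative hazard functions will be provided". The SAS code there is PROC LIFETEST with a two-level indicator (event or right-censored), so death outside the endpoint has no code of its own. Protocol 10.3.3.1 has the same plan.

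SAP 4.5.3 groups the primary composite, its components, the secondary efficacy endpoints and bleeding as clinical event endpoints. Its general rule for patients without the event, other than for CV death and all-cause mortality, is censoring "At the earlier date of last clinical event ascertainment date, date when patient died or ECOD". Protocol 10.3.3.5 likewise censors at a death that is not part of the endpoint.

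The method is extended to the secondary endpoints (SAP 6.2.6), to the components, MACE, MALE and landmark plots (6.2.8), and to bleeding as a cumulative event rate (6.4.5). The SAP names no cumulative incidence or other competing-risk method.

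The protocol synopsis reads differently: "Kaplan-Meier curves for the cumulative incidence risk and cumulative incidence functions will be provided". On benefit-risk, SAP 6.6 says "The benefit-risk evaluation will be based on the comparison of the time-to-first-event rates" and leaves the details to a separate supplement.

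**The concern.** A patient who has died can no longer have a limb revascularization, a hospitalization or a VTE. Kaplan-Meier with that death censored treats the patient as if still able to have the event at the same hazard as the survivors. The complement of the curve is then a hypothetical risk in a population without competing deaths, and it lies above the proportion of patients who actually have the event. The label *cumulative risk* is therefore wrong for such endpoints.

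Which deaths compete depends on the endpoint:
- primary composite, MACE and secondary 5: non-CV deaths;
- secondary 1: deaths other than coronary heart disease deaths;
- secondary 2 (unplanned index-limb revascularization), 3 (thrombotic hospitalization) and 7 (VTE), and MALE: essentially all deaths;
- the other single components and bleeding: deaths that are not themselves the event;
- secondary 4 and 6: none, because they contain all-cause death.

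At stake are the absolute risks that readers take from the curves, and any absolute effect measure later derived from them.

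**Working it through.** **1. The plan's own figure.** The documents give no cumulative risk to reproduce, so the design was checked first to confirm the planning hazards. Inputs from SAP 4.6: control rate 7.5% per year, HR 0.80, power 90%, one-sided alpha 0.025, the stated drug discontinuation, 1.5% per year loss or non-CV death, accrual 15/30/55% over 18 months, and 24 months of follow-up after the last patient. Without dilution, the Schoenfeld formula gives 4 × (1.960 + 1.282)² / (ln 0.80)² = 845 events after rounding up. With the stated discontinuation and loss, a Markov-type log-rank calculation on hazard 0.075 gives 1,014 events and 89.9% power at 6,500 patients. The plan's 1,015 events and 90% power are reproduced.

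**2. Formulas.** With constant event hazard l, competing-death hazard m and time t in years:
- one minus Kaplan-Meier = 1 − exp(−l·t)
- cumulative incidence = l/(l + m) × [1 − exp(−(l + m)·t)]

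**3. Primary composite, control arm, t = 3.5.** SAP 4.6 gives: "The annualized event rate in the control arm is approximately 7.5% per year". Its 1.5% per year covers loss to follow-up and non-CV death together, so it is an upper bound for the competing hazard under the planning assumptions.
- Kaplan-Meier: 1 − exp(−0.2625) = 23.09%.
- Cumulative incidence, m = 0.015: 0.8333 × (1 − exp(−0.315)) = 22.52%.
- Cumulative incidence, m = 0.0075: 0.9091 × (1 − exp(−0.28875)) = 22.80%.
- Excess: 0.3-0.6 points, or 1.3-2.5% in relative terms. At 30 months with m = 0.015: 17.10% against 16.79%.

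**4. An endpoint without a death component, t = 3.5.** The event rate of 4% per year is the limb-event rate in protocol 10.4. The documents give no trial-wide death rate, so 2-10% per year is assumed; the top of the range follows the roughly 10% one-year mortality for critical limb ischemia in protocol 3.1. Kaplan-Meier gives 1 − exp(−0.14) = 13.06% throughout. The risk differences use HR 0.80, equal mortality in both arms and no dilution from stopping drug; the Kaplan-Meier difference is 2.47 points throughout.

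| Deaths per year | Cumulative incidence | KM excess, points | Relative excess | Risk difference from cumulative incidence, points |
|---|---|---|---|---|
| 2% | 12.63% | 0.44 | 3.5% | 2.39 |
| 4% | 12.21% | 0.85 | 7.0% | 2.31 |
| 6% | 11.81% | 1.25 | 10.6% | 2.24 |
| 10% | 11.07% | 2.00 | 18.0% | 2.10 |

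The relative excess hardly depends on the event rate. With the same assumed mortality range, an assumed 0.5% per year event gives 1.73% against 1.68-1.46%, and an assumed 8% per year event gives 24.42% against 23.62-20.77%.

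**5. Direction of a risk difference.** For the primary with equal competing mortality at 1.5% per year, Kaplan-Meier gives 23.09 − 18.94 = 4.15 points and cumulative incidence gives 22.52 − 18.47 = 4.05. With unequal mortality the sign of the error can change. For a 4% per year event, HR 0.80, and deaths of 4% per year on control and 5% on rivaroxaban, the cumulative incidence difference is 12.211 − 9.736 = 2.475 points against 2.469 from Kaplan-Meier. In the cases examined, the crossover came at a rivaroxaban-to-control mortality ratio of about 1.21-1.24.

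**The case against.** The strongest reply is that the SAP uses Kaplan-Meier for a limited purpose, to show the timing and consistency of the effect, and that the treatment effect is the hazard ratio. The hypotheses are stated on survival functions, which Kaplan-Meier displays. Deaths count as CV unless a non-CV cause is clearly shown (protocol 9.4.2), which limits competing deaths for the primary. All of this stands. It is why the excess on the primary is small and why the plots should stay. It does not make the risk label right for revascularization, hospitalization, VTE or MALE.

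A reader might infer four stronger things that the documents do not support:
- *That planned risk differences are overstated.* The SAP plans no risk difference or number needed to treat. One derived from these curves would be overstated, and the number needed to treat understated, if competing mortality is similar in the arms or lower on rivaroxaban; otherwise the direction can reverse.
- *That the benefit-risk results will be biased.* SAP 6.6 does not name Kaplan-Meier, and its rates could be person-time rates. The supplement is not among the documents.
- *That the SAP abandons a protocol commitment.* The synopsis sentence can be read as Kaplan-Meier curves for both quantities, and protocol 10.3.3.1 names cumulative hazard functions, which the SAP follows. The inconsistency lies within the protocol.
- *That Kaplan-Meier should be replaced everywhere, including on-treatment bleeding.* That analysis is capped at two days after last dose, so a competing-death correction alone would still not give the actual bleeding risk.

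**Conclusion.** The concern holds for the absolute-risk estimates only. Wherever deaths outside the endpoint occur, one minus Kaplan-Meier as planned overstates the actual cumulative risk. At 42 months the excess is at most about 0.6 points for the primary under the plan's own rates. For a 4% per year endpoint without a death component it is about 0.4-2.0 points.

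The primary figure rests on constant hazards and on non-CV death making up half to all of the 1.5% per year. The second range rests on constant hazards and an assumed mortality of 2-10% per year. The direction of the excess in each arm does not depend on these assumptions; its size does. The stratified log-rank test and Cox hazard ratio remain valid as cause-specific analyses, and nothing in the confirmatory testing, power or event target changes. The correction is worth making because it is cheap and removes a known bias from the reported absolute risks.

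**What to change.** 1. In SAP 6.2.5, 6.2.6 and 6.2.8, add Aalen-Johansen cumulative incidence curves and estimates by arm for every ITT-scope endpoint that does not include all-cause death, with death outside the endpoint as the competing event. This needs a third level in the event indicator.
2. In SAP 6.4.5, do the same for the ITT-scope and overall-duration bleeding analyses.
3. Keep the Kaplan-Meier plots as the display that accompanies the log-rank test, but do not call them cumulative risk for these endpoints. Leave the log-rank and Cox analyses unchanged.
4. State that any reported absolute risk or risk difference, including any in the benefit-risk supplement, is based on the cumulative incidence estimates.
5. Reconcile the synopsis (cumulative incidence functions) with protocol 10.3.3.1 (cumulative hazard functions).

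The cost is SAP and table-shell wording and minor programming. The reported absolute risks become slightly smaller.

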6.2.6 Analysis of secondary efficacy variables

If the primary efficacy outcome is statistically significant, the secondary efficacy outcomes will be tested in a sequential manner according to the order as listed in Section 6.2.2 with one-sided alpha of 0.025. If an individual test during any step is not statistically significant, further treatment comparison may continue (i.e., reporting of p-values) but significance will not be claimed. This hierarchical testing procedure will control the global Type 1 error level.

Statistical Analysis Plan

Protocol No.: **BAY 59-7939 / 17454**

Page: 22 of 36

The analysis of the secondary variables will be based on the ITT analysis set and ITT data scope, including events as adjudicated by the ICAC or reported by investigators if not being adjudicated.

The statistical hypotheses for the secondary efficacy outcomes are defined similarly as for the primary efficacy outcome. The analysis methods will be similar to those described for the primary efficacy outcome.

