4.4 Interim Analyses and Data Monitoring

The Independent Data Monitoring Committee (IDMC) will monitor the study for greater than expected efficacy and for safety. There will be one formal pre-planned interim analysis to assess greater than expected efficacy, which will be performed when approximately 67% of the planned primary efficacy outcome events (~680) have accrued and are adjudicated. Based on that analysis, the study may be stopped early, if there is overwhelming superiority of rivaroxaban ($p<0.001$, 2-sided) for the primary efficacy endpoint (following the Haybittle-Peto approach) ([Haybittle 1971](#)). Details on the approach to the interim analyses and refinement of decision rules are specified in the IDMC charter.

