4.5 Data Rules

4.5.1 Analysis Dates

For the study, the following date and time window are of relevance for the analysis:

- Efficacy cut-off date:
The trial is designed to be terminated when 1015 patients have experienced a confirmed primary efficacy outcome event. The ECOD is a predicted common date when at least 1015 primary efficacy outcomes are expected to have occurred. It is the last calendar date acceptable for counting events for the primary analysis.
- Trial close-out window:
The time period when all subjects return to the clinic for an EOT visit. All randomized subjects should return for their EOT visit after the ECOD.

For each subject, the following individual dates are of relevance for analysis:

- Randomization date:
The date of randomization as recorded in the IxRS system.
- EOT Visit date:
The date of the EOT visit. If subjects do not have an EOT visit, the date will be missing.
- Date of last contact:
The date of the last documented contact with the subject or a third party (including data on subject survival status, see [Appendix A](#) for details).
- Date of first dose of study treatment:
The date of the first dose of rivaroxaban or rivaroxaban placebo, defined as:
 - Date of first dose from the appropriate CRF page capturing the study medication (rivaroxaban or rivaroxaban placebo) if this date is complete.
 - Date of the earliest logically possible dose of study medication (rivaroxaban or rivaroxaban placebo) administration in cases where the date of first dose is missing or incomplete. See [Appendix D](#) for details of the imputation rules.
- Date of last dose of study treatment:

Statistical Analysis Plan

Protocol No.: **BAY 59-7939 / 17454**

Page: 11 of 36

The date of the last dose of rivaroxaban or rivaroxaban placebo, defined as:

- Date of last dose from the appropriate CRF page capturing the study medication (rivaroxaban or rivaroxaban placebo) if this date is complete.
- Date of the latest logically possible dose of study medication (rivaroxaban or rivaroxaban placebo) administration in cases where the date of last dose is missing or incomplete. See [Appendix D](#) for details of the imputation rules.

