4.5.2 Data Scopes

All analyses are based on two elements:

- 1) *analysis set*, which specifies which subjects will be included in an analysis; and
- 2) *data scope*, which specifies the time window within which data will be included in an analysis.

This section describes the coverage of the event *data scopes* used for the statistical analyses. *Analysis sets* are described in Section 5.

Data scope according to intention-to-treat principle (ITT)

The ITT data scope includes outcome events observed from randomization date until the ECOD. Events occurring after the ECOD will not be counted for primary analysis. This ITT data scope will be applied mainly to the analyses of efficacy variables.

Data scope according to treatment (on-treatment)

The on-treatment data scope will include all outcome events observed from randomization until 2 days following permanent discontinuation of the study drug. This on-treatment data scope will be applied mainly to the analyses of safety variables (e.g. bleeding).

Data scope according to overall study duration for sensitivity analysis

The overall study duration data scope will include all outcome events observed from randomization until the last contact/visit. This data scope will be applied for sensitivity analysis only.

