6.2.2 Secondary efficacy variables

The secondary efficacy variables of this study are:

- time from randomization to the first occurrence of MI, ischemic stroke, coronary heart disease mortality, ALI, and major amputation of a vascular etiology
- time from randomization to the first occurrence of an unplanned index limb revascularization for recurrent limb ischemia (subsequent index leg revascularization that was not planned or considered as part of the initial treatment plan at the time of randomization)
- time from randomization to the first occurrence of hospitalization for a coronary or peripheral cause (either lower limb) of a thrombotic nature
- time from randomization to the first occurrence of MI, ischemic stroke, all-cause mortality, ALI, and major amputation of a vascular etiology
- time from randomization to the first occurrence of MI, all-cause stroke, CV death, ALI, and major amputation of a vascular etiology
- time from randomization to the first occurrence of all-cause mortality
- time from randomization to the first occurrence of VTE events

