Appendix A: Study Closeout Procedure and Variables used for Censoring

Note: The dates and timeline shown are for illustration purpose only. ECOD= Efficacy cut-off date, EOT Visit=end of treatment visit, PS-FU Visit=Post-study treatment follow-up visit (phone call), DBL=database lock

The executive committee will monitor the accrual of the number of primary events, and when appropriate predict and define an ECOD at which time the pre-defined target number of events for the primary composite endpoint are expected to have occurred. All randomized patients should return for their End of Treatment (EOT) visit after the ECOD.

Events that occur after the ECOD will also be collected and adjudicated. These events will be included in sensitivity analyses but not the primary analysis.

For the implementation of the censoring rules below variables are defined to distinguish between a patient's last contact with information relating to clinical events versus CV-death / all-cause mortality.

- Date of objection to further data collection

This date will be given only for those subjects who expressed objection to further data collection after withdrawal of informed consent.

- Last clinical event ascertainment date

The latest date from regular or unscheduled post-randomization visits or contacts with assessment of clinical events or latest adjudicated clinical event start date.

- Date of last contact alive

The date of the last documented contact with the subject or a third party (including data on subject survival status) derived from the maximum (last clinical event ascertainment date, SAEs date, vital status date, consent withdrawn date or date of objection to further data collection). The resulting maximum date is capped by the death date if the patient died or by the date of clean database. In addition, the date of last contact alive will be the day before the death date, if available, for subjects who die.

Statistical Analysis Plan

Protocol No.: **BAY 59-7939 / 17454**

Page: 33 of 36

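### SAP 6.2.6 claims global Type 1 error control without condition, but one-sided 0.025 reused for the secondaries after an interim stop exceeds its level modestly

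*SAP*

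**What the plan says.** **Level and claim.** Under SAP 6.2.6, a significant primary opens the secondary tests, which run "according to the order as listed in Section 6.2.2 with one-sided alpha of 0.025". No separate level is given for a primary that succeeds at the interim. The section concludes, without condition: "This hierarchical testing procedure will control the global Type 1 error level".

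**Interim.** SAP 4.4 plans one interim analysis at about 67% of the events (about 680), at which "the study may be stopped early, if there is overwhelming superiority of rivaroxaban", meaning two-sided p<0.001 on the primary endpoint. Protocol 10.5 has the same rule, makes no alpha adjustment at the final analysis because little is spent at the interim, and adds that secondary efficacy and safety will be taken into account. SAP 4.4 also says: "Details on the approach to the interim analyses and refinement of decision rules are specified in the IDMC charter".

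**Data cut.** The secondaries use the ITT data scope, and "The ITT data scope includes outcome events observed from randomization date until the ECOD" (SAP 4.5.2). The efficacy cut-off date (ECOD) is tied to the event target: "The ECOD is a predicted common date when at least 1015 primary efficacy outcomes are expected to have occurred" (SAP 4.5.1). Appendix A has the executive committee "predict and define an ECOD at which time the pre-defined target number of events for the primary composite endpoint are expected to have occurred". Neither place says what the ECOD becomes after an early stop.

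**First secondary.** It is the "time from randomization to the first occurrence of MI, ischemic stroke, coronary heart disease mortality, ALI, and major amputation of a vascular etiology" (SAP 6.2.2), which is the primary composite with coronary heart disease death in place of CV death.

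**The concern.** A fixed-sequence procedure controls the familywise error when each hypothesis is tested once, at a time that does not depend on the data. Here the primary result decides whether a secondary is tested at about 67% or at 100% of the information, and the secondary is correlated with the primary. Giving the secondary the full 0.025 at whichever look occurs lets part of its error be spent twice. The reason for making no final adjustment, that little alpha is spent at the interim, holds for the primary but not for a secondary tested at 0.025 there.

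What is at stake is the confirmatory standing of the ordered secondary claims after an early stop. Such a stop is realistic: at the effect giving 90% power, the primary crosses the interim boundary with probability 26%. That figure describes the primary in general, not the case where the first secondary is null. Separately, the data cut after a stop would be chosen once the interim result is known, unless the charter already fixes it.

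**Working it through.** **Inputs from the documents.** Target 1,015 events, interim about 680, so t = 680/1015 = 0.670. Interim boundary one-sided 0.0005 (z = 3.2905). Final primary level and secondary level one-sided 0.025 (z = 1.960). Power 90%.

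**Assumed, not in the documents.** The correlation rho between the primary and secondary statistics (0.3 to 0.8), the same information fraction for the secondary as for the primary, and a boundary crossing treated as a stop.

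**The plan's own figures.** 0.67 x 1,015 = 680. With the stated accrual, discontinuation and loss, and 7.5% per year read as a hazard, a piecewise log-rank calculation gives 1,014 events and 89.9% power, so the design reproduces. For the primary over both looks, 1 - P(Z1 <= 3.2905, Z2 <= 1.960) with correlation sqrt(0.670) = 0.8185 is 0.02503. The excess over 0.025 is negligible.

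**Chance of an interim crossing.** The 90%-power drift at the final is 1.960 + 1.2816 = 3.2415. At the interim it is 3.2415 x 0.8185 = 2.653. P(Z > 3.2905 - 2.653) = P(Z > 0.637) = 0.26.

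**Error for a true-null secondary.**

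Error = P(Z1p > 3.2905, Zs,cut > 1.960) + P(Z1p <= 3.2905, Z2p > 1.960, Z2s > 1.960)

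Correlation is rho between endpoints at the same look, and the square root of the information ratio within an endpoint. For rho = 0.5 at the 90%-power effect, with the cut at the interim, the two terms are 0.0182 and 0.0091, which sum to 0.0272 before rounding.

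| rho | 1,015 events only, maximum | Cut at interim, 90%-power effect | Cut at interim, maximum over primary effects | Cut at 80%, maximum | Cut at 90%, maximum |
|---|---|---|---|---|---|
| 0.3 | 0.0250 | 0.0258 | 0.0261 | 0.0256 | 0.0252 |
| 0.5 | 0.0250 | 0.0272 | 0.0272 | 0.0262 | 0.0255 |
| 0.7 | 0.0250 | 0.0278 | 0.0288 | 0.0270 | 0.0259 |
| 0.8 | 0.0250 | 0.0275 | 0.0299 | 0.0275 | 0.0261 |

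With the documents' accrual, event and loss rates and HR 0.80 throughout, event 680 falls at month 31.3, 80% information at month 35.5 and 90% at month 38.8. The later cuts are therefore about 4 and 7.5 months after event 680.

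**First secondary.** If it is null, the primary can differ between arms only through the CV deaths it does not share. Let rho squared be the share of common events, so that the primary log HR = (1 - rho squared) x log HR of the non-shared events. With HR 0.80 on those events:

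| rho | Primary HR | Interim crossing | Error, cut at interim |
|---|---|---|---|
| 0.5 | 0.846 | 13.4% | 0.0269 |
| 0.7 | 0.892 | 3.5% | 0.0274 |
| 0.8 | 0.923 | 1.2% | 0.0266 |
| 0.9 | 0.958 | 0.3% | 0.0246 |

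Near rho 0.9 the excess is gone, because the primary itself then rarely opens the gate.

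**Repairs, cut at the interim, worst case over primary effects for rho 0.3 to 0.8.** One-sided 0.0005 after an interim stop and 0.025 at the final gives about 0.017 to 0.020. An O'Brien-Fleming-type boundary (0.0062 at 67%, 0.0231 at the final) gives 0.017 to 0.021. Both stay below 0.025.

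**The case against.** The strongest defence is that the only data cut the documents define is the one at 1,015 events, where the claim is correct. The failure needs a contingency that is not written out, and the SAP assigns interim details to a charter that may settle both level and cut. This stands as a limit on what can be concluded. It does not rescue the sentence, because 6.2.6 is conditioned on primary significance and not on the final analysis, and it makes its claim without citing the charter.

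It is also fair that a cut exactly at event 680 is the extreme case. Interim events must first be adjudicated, and the ECOD is a predicted date, so a real cut would probably come later and the excess would be smaller. The size depends on a correlation that must be assumed. For the heavily overlapping first secondary the excess may be nil. For later secondaries the tabulated figures are upper bounds, since every earlier test must be passed first.

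Three stronger readings are not supported:

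- A reader might infer that no secondary level exists for an early stop and that one would be picked after the interim result. SAP 6.2.6 does state a level, 0.025. Only the data cut is open.
- A reader might infer that the committee could stop selectively when a secondary also looks good, which would raise the error further. Protocol 10.5 says only that secondary efficacy will be considered and gives no such rule.
- A reader might take a higher correlation and quote a larger worst case, for example 0.0317 at rho 0.9. That maximum occurs at a primary HR near 0.88. For a null first secondary in the nested model this requires an HR of about 0.88^(1/0.19) = 0.51 on the non-shared deaths, which nothing in the documents suggests.

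**Conclusion.** The unconditional statement in SAP 6.2.6 is correct at the planned 1,015-event analysis. It is not correct if, as the text literally reads, 0.025 is used for the secondaries on data cut at or near an interim stop. The excess is modest: 0.026 to 0.028 against 0.025 at the 90%-power effect, and at most 0.026 to 0.030 over all primary effects with a cut at the interim. It falls to at most 0.0275 with a cut at 80% information and 0.0261 at 90%.

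These figures rest on assumed correlations of 0.3 to 0.8, equal information fractions, and a crossing that leads to a stop. Neither the primary analysis nor a trial that runs to its target is affected. The undefined ECOD after an early stop is a separate gap that does not depend on the calculation. The unseen IDMC charter may close both. This is a minor correction to the SAP and does not threaten the trial's main conclusion.

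**What to change.** 1. **SAP 6.2.6.** Pre-specify a secondary boundary for an interim stop, consistent with the IDMC charter, or cite the charter if it already has one. Two workable choices are (a) one-sided 0.0005 in order after an interim stop and 0.025 at the final, or (b) an O'Brien-Fleming-type boundary, about 0.0062 at 67% information and 0.0231 at the final, recomputed at the information fraction of the actual cut. With either in place the Type 1 error sentence can stay. Otherwise, limit that sentence to the 1,015-event analysis.
2. **SAP 4.5.1 and Appendix A.** State how the ECOD is set after an early stop.

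**Cost.** Two or three sentences, plus less power for the secondaries after an early stop. As an illustration, assume 200 to 400 secondary events at the stop and HR 0.80. Power, Phi(0.2231 x sqrt(events/4) - z), is then 4 to 15% at 0.0005, 18 to 39% at 0.0062 and 35 to 61% at 0.025. Mortality and VTE would suffer most under 0.0005. Choice (a) costs nothing if the trial runs to 1,015 events. Choice (b) makes the final secondary level slightly stricter and needs an information fraction for each secondary.
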